9.4.6.1.1 Analysis of Treatment-Emergent Adverse Event Rates per 100 Patient-years of Follow-up

Summaries of TEAEs occurring in subjects in the safety population of this OLE study will also be provided based on combined AE data from the core studies and the OLE study, attributing each TEAE to the last study treatment received at/before the AE onset. In other words, an AE will be defined as treatment-emergent under a given study treatment (OKZ 64 mg q4w, OKZ 64 mg q2w, placebo, or adalimumab) if AE's onset date is on or after the date of first dose the corresponding treatment and prior to initiation of the next study treatment, if any (e.g., OKZ after placebo or adalimumab). In order to account for differences in the duration of exposure and follow-up under each study treatment and across subjects, subject IRs and ERs will be summarized per 100 subject-years (SY) of follow-up (/100 SY) based on the OLE safety population and presented by study treatments as follows:

- i. OKZ 64 mg q4w: subjects receiving OKZ 64 mg q4w during the core study or OLE. Only those TEAEs that first occur or worsen in severity after the first administration of OKZ 64 mg q4w (either in the core or OLE study) will be counted.
- ii. OKZ 64 mg q2w: subjects receiving OKZ 64 mg q2w during the core study or OLE. Only those TEAEs that first occur or worsen in severity after the first administration of OKZ 64 mg q2w (either in the core or OLE study) will be counted.
- iii. Placebo: subjects receiving placebo during the core study. Only those TEAEs that first occur or worsen in severity after the first administration of placebo and prior to administration of OKZ will be counted. Subjects are considered as receiving placebo during the core study if they are receiving placebo as their overall study treatment, and not as monthly placebo injections administered to maintain the blind in the OKZ 64 mg q4w group.
- iv. Adalimumab: subjects receiving adalimumab as active control study treatment during the core study CL04041023. Only those TEAEs that first occur or worsen in severity after the first administration of adalimumab and prior to administration of OKZ will be included.

The following summaries will be provided:

- IRs (/100 SY) and ERs (/100 SY) for TEAEs overall and by SOC
- IRs (/100 SY) and ERs (/100 SY) for SAEs overall and by SOC and PT
- IRs (/100 SY) and ERs (/100 SY) for AESIs overall and by SOC and PT
- IRs (/100 SY) and ERs (/100 SY) for (adjudicated) MACE and individual MACE components
- IRs (/100 SY) and ERs (/100 SY) for most frequent TEAEs (PT level IRs [/100 SY] ≥5.0 in any treatment group) by SOC and PT

IRs/100 SY for each specific AE term (referred to as "event" for brevity) under treatment j, corresponding to treatments (i) – (iv) described above, will be calculated as follows:

$$IR_j (/100 SY) = s_j / \sum_i c_{i,j}$$

where s_j is the number of subjects with the event that is treatment-emergent under treatment j, and $c_{i,j}$ is a truncated follow-up time (in 100-year units) for subject i and treatment j (i.e., the time from the subject's date of first dose of treatment j to the date of first occurrence of the event after start of treatment j or end of follow-up period for treatment j, whichever

occurs earlier). For OKZ treatments (OKZ 64 mg q4w and q2w), the end of follow-up period will be the date of last dose of OKZ treatment plus 155 days (5 half-lives of study treatment) or last contact with the subject, whichever occurs earlier. For placebo and adalimumab treatments, the end of follow-up period will be the day before the start of OKZ treatment.

ERs (/100 SY) for each specific AE term under treatment j will be calculated as follows:

$$ER_j(100 SY) = \sum_i v_{i,j} / \sum_i t_{i,j}$$

where $v_{i,j}$ is the number of treatment-emergent events that the subject i experiences under treatment j, and $t_{i,j}$ is a total follow-up time (in 100-year units) of subject i for treatment j, i.e., from the date of subject's first dose of treatment j to the end of follow-up period for treatment j. For OKZ treatments (OKZ 64 mg q4w and q2w), the end of follow-up period will be the date of last dose of OKZ treatment plus 155 days (5 half-lives of study treatment) or last contact with the subject, whichever occurs earlier. For placebo and adalimumab treatments, the end of follow-up period will be the day before the start of OKZ treatment.

Assuming the event process is Poisson distributed, exact $100*(1-\alpha)\%$ confidence intervals for IR_i (/100 SY) and ER_i (/100 SY) will be calculated as follows (Sahai and Khurshid, 1993):

Lower confidence limit:
$$LCL = \frac{\chi^2_{\alpha/2,2D}}{2E}$$
 for D>0, 0 otherwise,

Upper confidence limit
$$UCL = \frac{\chi^2_{1-\alpha/2,2D+2}}{2E}$$

where $\chi^2_{\alpha,k}$ is the α^{th} quantile of the Chi-square distribution with k degrees of freedom, and the D and E are the numerator and denominator of the rate.

Summaries of IR_j (/100 SY) and ER_j (/100 SY) for the OKZ treatments (i) and (ii) may be further subdivided into 2 subgroups: subjects receiving adalimumab in the core study CL04041023 versus all other subjects.

In addition to the above summaries of rates/100 SY, a plot of cumulative mean function (CMF) across study follow-up time will be produced for selected types of events for each treatment (i) – (iv). The cumulative mean function at each time point t represents an estimated mean number of recurrent events expected by time t in a treatment group (Siddiqui, 2009; Nelson, 2003). Plots of CMF will be produced for SAEs overall and by SOC, AESIs overall and by SOC, as well as MACEs.

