- All AEs (and SAEs) will be solicited at every study visit, recorded, and coded according to the most recent version of the Medical Dictionary for Regulatory Activities (MedDRA)
- Vital signs and physical examination findings
- Laboratory parameters
- Electrocardiogram (ECG) and other specialized test findings

Changes from OLE Baseline value in safety parameters will be summarized based on the definition of OLE Baseline value as the last available measurement prior to the first OLE dose of study treatment. Additionally, changes from Core Baseline will be summarized based on the baseline value from the core study (i.e., the last available measurement prior to the first dose of study treatment in the core study). For subjects from Study CL04041025 who initiate OKZ treatment at Week 16 of the core study after having completed 16 weeks of placebo treatment, changes from the last pre-OKZ value will also be summarized.

All AEs will be analyzed in terms of descriptive statistics and qualitative analysis. Adverse events will be summarized in terms of incidence during the OLE study, as well as overall during the core studies and the OLE study. Adverse events will be listed for each subject and summarized by system organ class (SOC) and preferred term (PT) according to the most recent version of the MedDRA. In addition, summaries of AEs by severity and relationship to study treatment will be presented. Follow-up-adjusted incidence rates and event rates per 100 subject-years of follow-up over the course of the core study and the OLE will be summarized by treatment group for SAEs and AESIs. All safety and tolerability data recorded during the study will be listed and summarized by treatment group in both the core study and the OLE, and over time, as appropriate.

The above collected clinical database will be summarized and presented with particular focus on the following safety concerns identified as AESIs based either upon the safety data available to date (refer to the most recent version of the Investigator's Brochure) for OKZ or drug class-related events for a biologic, including IL-6 inhibitors:

- Infections (particularly serious infections), tuberculosis, opportunistic infections
- Malignancies
 - The Investigator will be asked to provide relevant medical information/documentation (e.g., pathology/histology reports) on all the malignancies cases, whether considered serious or not, as these cases will be recorded in the safety database.

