4.1 Safety Endpoints

The following safety endpoints will be evaluated:

- Nature, incidence, severity, and outcome of AEs, including SAEs and AEs of special interest (AESIs)
- Follow-up-adjusted incidence rates (IR) and event rates (ER) (per 100 subject-years [SY] of follow-up) for SAEs and AESIs
- Proportions of subjects with clinically significant laboratory abnormalities
- Assessment of changes over time in clinical laboratory parameters, vital sign measurements, and physical examination findings
- Time from first exposure to OKZ to the first occurrence of any major adverse cardiac event (MACE)
- Incidence and titer of antidrug antibodies (ADAs) to OKZ, incidence of neutralizing antibodies, and the time course of antibodies

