9.4 Statistical Methods

This section provides a high-level description of the analyses planned in this study. Details of any analysis, interim or final, will be specified in the SAP, to be written and finalized prior to database lock. The statistical analysis will be performed by R-Pharm International's designee. All statistical analyses will be conducted using SAS® version 9.2 or higher for Windows.

All data collected in the clinical database will be presented in subject data listings.

Data collected after the modification of background therapy (as described in Section 6.13.3) will be used in all analyses.

Data collected during the core studies for subjects enrolled in the OLE study may be programmatically combined with the OLE study database for selected analyses.

All analyses of safety and efficacy will be descriptive; no inferential analyses will be performed.

Continuous endpoints will be summarized using descriptive statistics such number of available values (n), mean, median, minimum, maximum, and standard deviation in each treatment group and overall, as appropriate. Categorical endpoints will be summarized by the number and percentage of subjects in each category.

Data will be summarized based on treatment groups reflecting randomized or actual treatment (for efficacy or safety analyses, respectively) during the core and OLE studies as follows:

- a. OKZ 64 mg q4w (OLE): All subjects in the OKZ 64 mg q4w group in the OLE
- b. OKZ 64 mg q2w (OLE): All subjects in the OKZ 64 mg q2w group in the OLE
- c. OKZ 64 mg q4w (core/OLE): Subjects from the OKZ 64 mg q4w group in the core study and continuing on OKZ 64 mg q4w in OLE. For subjects enrolling from the CL04041025 core study, inclusion in the OKZ 64 mg q4w group in the core study will be based on the initial treatment period prior to Week 16 (i.e., placebo subjects re-randomized to receive OKZ 64 mg q4w at Week 16 will not be included in this group).
- d. OKZ 64 mg q2w (core/OLE): Subjects from the OKZ 64 mg q2w group in the core study and continuing on OKZ 64 mg q2w in OLE. For subjects enrolling from the CL04041025 core study, inclusion in the OKZ 64 mg q2w group in the core study will be based on the initial treatment period prior to Week 16 (i.e., placebo subjects

re-randomized to receive OKZ 64 mg q2w at Week 16 will not be included in this group).

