9.4.6.1.2 Time to First Major Adverse Cardiovascular Event

For MACEs and individual components of MACE, time from the first dose of OKZ to first event will be summarized using a Kaplan-Meier product limit method. This analysis will be

based on the OLE Safety population using combined data from the core studies and the OLE study.

Time to first event will be computed for each specific type of event (MACE overall and individual components of MACE) as the number of days between the subject's date of first dose of OKZ treatment either in the core or OLE study and the onset of the first event that is treatment-emergent under the OKZ treatment. Subjects not experiencing an event of interest during the follow-up period associated with the OKZ treatment will be censored at the date of last contact.

Summaries will be presented by treatment groups, as defined in Section 9.4. Summaries will include plots of the estimated survival curves using the Kaplan-Meier method as well as Kaplan-Meier cumulative estimates of event-free rates at time points corresponding to 6, 12, 18, 24, and 30 months after initiation of OKZ treatment. Pointwise confidence intervals for these estimates will be computed using the log-log transformation method. Kaplan-Meier estimates of mean event-free time and its log-log transformed confidence interval in each treatment group will also be produced. A time limit of 127 weeks will be used for the estimation of mean event-free time if the largest observed time in data is censored. Descriptive statistics for the number of subjects with event, censored, and duration of follow-up for censored subjects will be provided.

Additional details will be provided in the SAP.

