9.4.6.1.3 Time to First Malignancy

Analysis of time from the first dose of OKZ to the first malignancy will also be conducted using the Kaplan-Meier method in a similar manner as will be done for MACE (see Section 9.4.6.1.2).

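### Combined core-plus-extension safety rates and curves count core time only for subjects who later entered the extension, so events that prevent entry are under-counted, most of all in the placebo and adalimumab columns

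*Combined protocol and SAP*

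**What the plan says.** Section 9.3 of the protocol defines the Safety population by at least one dose in the OLE. Section 9.4.6.1.1 uses that population for incidence rates (IR) and event rates (ER): "Summaries of TEAEs occurring in subjects in the safety population of this OLE study will also be provided based on combined AE data". It presents four columns: OKZ q4w, OKZ q2w, placebo and adalimumab. Each OKZ column pools everyone who took that regimen in the core study or the OLE, counted from the first dose of it. For the comparators: "For placebo and adalimumab treatments, the end of follow-up period will be the day before the start of OKZ treatment". For the same four treatments, "a plot of cumulative mean function (CMF) across study follow-up time will be produced for selected types of events".

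The MACE Kaplan-Meier analysis in 9.4.6.1.2 runs from the first OKZ dose and is "based on the OLE Safety population using combined data from the core studies and the OLE study". Section 9.4.6.1.3 follows suit: "Analysis of time from the first dose of OKZ to the first malignancy will also be conducted using the Kaplan-Meier method". Both are shown by the ten groups (a) to (j) of section 9.4. That section also says: "Data collected during the core studies for subjects enrolled in the OLE study may be programmatically combined with the OLE study database". The synopsis describes the SAE and AESI rates as "per 100 subject-years of follow-up over the course of the core study and the OLE".

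OLE entry is selective. Section 5.3.1 requires completion of the 24-week core treatment period. Section 5.3.2 lets the investigator exclude a subject for medically important core-study conditions, with SAEs, frequent AEs and serious infections among the examples, and bars anyone with evidence of active tuberculosis (TB). Section 7.4.9 also bars a subject with a new active TB diagnosis at Visit 1.

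**The concern.** Subjects are selected on what happened during the core study, and the same core time then enters the numerators and denominators. A subject who died, withdrew after a serious event, or was refused entry because of one contributes neither the event nor the time. Events that have no bearing on rollover are not affected.

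The selection is unequal across columns of one table. Placebo and adalimumab follow-up ends before OKZ starts, so every day of it precedes OLE entry. Most OKZ follow-up comes after entry. Side by side, the comparator rates and cumulative mean function (CMF) curves are depressed more than the OKZ ones, which can suggest an OKZ excess that selection created. Absolute OKZ rates are also somewhat low. The exact Poisson intervals in 9.4.6.1.1 reflect random error only and would not reveal this.

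This matters because long-term safety is the primary objective, and section 4.1 lists both the follow-up-adjusted SAE and AESI rates and the time to first MACE as safety endpoints.

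**Working it through.** **The plan's own durations.** Five half-lives of 31 days (section 5.2.2) give 5 × 31 = 155 days, or 22.1 weeks, which matches 9.4.6.1.1. OKZ treatment lasts 24 + 82 = 106 weeks for core OKZ subjects and 8 + 82 = 90 weeks for CL04041025 placebo subjects, which matches 5.2. With a last dose at Week 104, OKZ follow-up ends at about Week 126. It therefore spans 126 weeks in groups c/d, 126 − 16 = 110 in g/h, and 126 − 24 = 102 in e, f, i and j.

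**Share f of follow-up that precedes OLE entry.**
- Placebo and adalimumab: f = 1.
- Groups c/d: 24/126 = 0.190. Groups g/h: 8/110 = 0.073. Groups e, f, i, j: 0.
- Pooled OKZ column: with x the share of subjects from core OKZ arms and y the share from the CL04041025 placebo arm, f = (24x + 8y)/(126x + 110y + 102(1 − x − y)). The documents do not give x and y. Assuming x = 0.5, y = 0 gives 12/114 = 0.105; x = 0.8, y = 0.1 gives 20/122 = 0.164.

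**Effect on rates.** Let q be the assumed share of core events that keep the subject out of the OLE, equal in all arms. Before entry the observed rate is (1 − q) times the true rate, so a column shows 1 − fq of true. With a true ratio of 1, the apparent OKZ-to-placebo ratio is (1 − fq)/(1 − q). For f from 0.164 to 0.105:

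| q | Placebo, observed/true | Pooled OKZ, observed/true | Apparent ratio |
|---|---|---|---|
| 0 | 1.00 | 1.00 | 1.00 |
| 0.10 | 0.90 | 0.98-0.99 | 1.09-1.10 |
| 0.25 | 0.75 | 0.96-0.97 | 1.28-1.30 |
| 0.50 | 0.50 | 0.92-0.95 | 1.84-1.89 |

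For example, at q = 0.25 and f = 0.164: (1 − 0.041)/0.75 = 0.959/0.75 = 1.28. At q = 1, which applies to death before entry, the comparator columns show zero by construction.

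**Sensitivity.** If q differs by arm, the ratio is (1 − f·q_OKZ)/(1 − q_placebo). It falls below 1 only when q_OKZ exceeds q_placebo/f, that is 1/0.164 = 6.1 to 1/0.105 = 9.5 times q_placebo. Early stopping raises f and lowers that multiple. For c/d alone with a last dose at Week 52, f = 24/(52 + 22) = 0.324 and the multiple is 3.1.

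**Effect on the Kaplan-Meier curves.** For a rare event with constant hazard and w pre-OLE weeks on the clock, the event probability at T weeks is about 1 − q·w/T of true. At q = 0.10 / 0.25 / 0.50:
- 6 months (T = 26): c/d (w = 24) 0.91 / 0.77 / 0.54; g/h (w = 8) 0.97 / 0.92 / 0.85.
- 24 months (T = 104): c/d 0.98 / 0.94 / 0.88.

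Groups e, f, i and j have no pre-OLE time on this clock. Aggregates a and b inherit the effect from the groups they contain.

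**The case against.** The strongest reply is that the plan handles this elsewhere and says openly whom it counts. Section 9.3 plans an ISS on all subjects in the core studies and the OLE. Section 9.4.6.1.1 names the OLE population, and section 9.4 makes every analysis descriptive. The primary objective concerns long-term OKZ safety, not a contrast with placebo or adalimumab. The OLE-only adverse event summaries in 9.4.6.1 are untouched, the absolute OKZ rates move little at moderate q, and the relative distortion runs against OKZ. The protocol also defers details to a SAP that is not in the supplied text and could add labels or delayed entry.

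Much of this stands, and it limits the severity. It does not remove the point. Section 9.3 keeps the ISS out of this study's report, so the ISS cannot correct the tables printed there. The OLE-only summaries give no rates per 100 subject-years. Naming the population does not tell a reader that the comparator columns consist wholly of time conditioned on later entry, and a side-by-side rate table is read as a comparison without any test. The population and the start and end of follow-up are fixed in the protocol itself, so the conclusion is limited to that wording.

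**Conclusion.** The point holds and should be fixed. The mechanism follows from the protocol text; the size does not. Every q above is an assumption, as are the subject mix, dosing to Week 104, constant hazards and equal q across arms. The model also leaves out the general selection of subjects who complete 24 weeks, which affects every group.

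Four stronger readings are tempting but unsupported:
- **Every core SAE blocks entry.** The first exclusion criterion rests on investigator judgement, so many will not.
- **The bias can be read from groups c/d.** Those groups are not columns of the rate tables, which pool them with subjects who have little or no pre-OLE OKZ time. The pooled figures are the relevant ones.
- **A fixed shortfall applies to active TB in the OKZ columns.** Active TB found before or at entry cannot appear in the comparator columns. Nothing in the documents separates it from TB arising later on OKZ, so no OKZ fraction can be given.
- **All deaths are missing MACE.** Section 7.4.4.2 lists death among potential events for adjudication, as defined in a charter that is not supplied. What is certain is that no death before OLE entry can be counted. A fatal event that began on placebo and ended in death after entry would still be counted under placebo.

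**What to change.** 1. Remove the placebo and adalimumab IR/ER columns and CMF curves from this report and refer to the ISS. If they stay, label them as conditional on OLE entry. Do not set comparators from all core-treated subjects beside OKZ rates restricted to OLE entrants: that would compare unselected with selected subjects and could favour OKZ.
2. Make OKZ IR/ER per 100 subject-years and CMF curves, with events and person-time from the first OLE dose, the main long-term results. Keep the combined core-plus-OLE OKZ rates as supportive, labelled as conditional on OLE entry.
3. Keep the MACE and malignancy Kaplan-Meier analyses from the first OKZ dose, labelled as conditional on OLE entry for groups a to d, g and h. Add a sensitivity analysis in which subjects join the risk set at the first OLE dose, by delayed entry or by starting the clock there. List first events from the core period separately.

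The cost is wording in 9.4.6.1.1 to 9.4.6.1.3, the matching synopsis text and the SAP, plus modest programming. No new data are needed, and the time-to-MACE endpoint stays. The main OKZ rates lose about 10-16% of subject-years under the assumptions above (more with early stopping), and early exposure in c/d moves to the supportive results. Rates from the first OLE dose still describe subjects selected for entry and should be presented as such.

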2.3 Rationale for the Study

The multicenter, open-label design used in this study is consistent with the precedent set for Phase III OLE trials of other biologics and is in accordance with health authority guidelines.

The goal of this Phase III study is to evaluate the long-term safety, tolerability, and efficacy of OKZ in subjects with moderately to severely active RA who previously completed

24 weeks of double-blind treatment with OKZ in the core studies. Olokizumab is expected to reduce the disease activity and induce an improvement in physical function. The study is expected to provide long-term safety information in a large group of subjects treated with OKZ for up to 106 weeks.

All subjects in this study will receive the first dose of OKZ at Week 24. For subjects transitioning from the adalimumab treatment group (core study CL04041023), there will be no additional time added for wash out of adalimumab other than the 2 weeks between the last dose of adalimumab in the core study (Week 22) and first dose of OKZ in the OLE study (Visit 1 [Week 24]). Similar approaches have been implemented in a number of other clinical studies involving adalimumab and other biologics or kinase inhibitors, and such a switch from one biologic to another is commonly observed in clinical practice without significant safety concerns (Bykerk et al, 2012; Furst et al, 2007; Schiff et al, 2009; Wollenhaupt et al, 2014). Despite this, the possibility for an increased risk of AEs, including infections, cannot be excluded (Humira® [adalimumab] Prescribing Information). This potential risk will be mitigated by closely monitoring all subjects throughout the OLE study.

It is possible that subjects assigned to the adalimumab treatment group in core study CL04041023 might achieve remission or a decrease in disease activity while being treated with adalimumab and switching to another biological treatment may lead to undesirable results for such subjects. However, it will not be known at the completion of the 24-week double-blind Treatment Period whether a subject was assigned to the adalimumab treatment group. Therefore, following a subject's completion of the core study and prior to enrollment in the OLE study, the Investigator and subject will decide jointly whether the subject will continue with the open-label administration of OKZ in this OLE study or exit the study.

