5.2.2 Safety Follow-up Assessments

Given the long half-life of OKZ (approximately 31 days), subjects will be followed up for approximately 5 OKZ half-lives (i.e., 22 weeks) after the final dose of study treatment.

For subjects remaining on randomized therapy until the last scheduled dose of study treatment, Visit 10 (EoT Visit) will be performed at Week 106 and extended Safety Follow-Up procedures will be performed at visits scheduled +4, +8, and +22 weeks after the last dose of study treatment (i.e., Visits SFU-1 [Week 108], SFU-2 [Week 112], and SFU-3 [Week 126], respectively).

Subjects who discontinue treatment early require a full safety assessment at Visit 10 (EoT/Week 106) (see Section 5.4.2), which will take place 2 weeks after the last study

treatment administration. These subjects will subsequently be followed for an additional 20 weeks (i.e., 22 weeks after the final dose of study treatment) during a Safety Follow-Up Period (see Section 5.4.3).

All subjects will be reminded of study contact information to report potential SAEs and are to inform the Investigator if they experience such events during the Safety Follow-Up Period (Section 7.4.5.4).

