7.4.3.2 Systemic Injection Reactions, Including Anaphylaxis

A systemic injection reaction is any untoward medical hypersensitivity-like event, other than injection site reactions, occurring during or after study treatment administration that can be at least possibly attributed to the study treatment. Systemic injection reactions are further classified as acute and delayed based on timing and presentation of symptoms typical for hypersensitivity reactions.

Acute and delayed reactions to the study treatment should be reported according to the judgment of the Investigator, based on the typical clinical features.

Any systemic allergic reaction that meets the criteria for seriousness should be reported as an SAE.

Subjects will be observed for AEs at the study site for at least 2 hours after the first administration of study treatment (Visit 1 [OLE Baseline/Week 24]) and for at least 30

minutes after the second administration of study treatment (Visit 2 [Week 26] for subjects receiving OKZ 64 mg q2w and Visit 3 [Week 28] for subjects receiving OKZ 64 mg q4w). For injections administered by the subject (or caregiver, if applicable), subjects will record in the Subject Diary (see Section 5.5) any complaints, signs, or symptoms that occur during or after the injection. Subjects will be asked to contact the Investigator if any significant reactions occur within the 2 hours following study treatment injection.

Acute injection reactions are usually defined as at least 1 of the following signs or symptoms occurring during or within 2 hours of the study treatment injection:

- Hypotension
- Urticaria
- Flushing
- Facial or hand edema
- Throat tightness, oral cavity, or lip edema
- Headache
- Shortness of breath.

The Investigator should report any AE of acute systemic injection reaction as "anaphylaxis" if it meets the Clinical Criteria for Diagnosing Anaphylaxis, as specified in Appendix 3 (Section 13.3).

The study site must have adequate arrangements to manage anaphylactic reactions.

Delayed injection reactions are usually defined as at least 2 of the following 4 signs or symptoms occurring within 1 day to 14 days following the injection:

- Rash
- Fever (more than 100°F [38°C])
- Polyarthralgias
- Myalgias.

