9.4.1 Definition of Baseline

Unless otherwise specified, data will be analyzed for changes from both Core Baseline and OLE Baseline values. The Core Baseline value for each parameter will be defined as the baseline value from the core study (i.e., the last available measurement prior to the first dose

of study treatment in the core study). The OLE Baseline value will be defined as the last available measurement prior to the first OLE dose of study treatment. For subjects from Study CL04041025 who receive placebo through Week 14 and are re-randomized to OKZ starting at Week 16 (groups [g] and [h] as defined in Section 9.4), additional analysis of change from the last pre-OKZ value (prior to the first dose of OKZ at Week 16) will also be performed.

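### Injection-reaction rates per 100 subject-years count OKZ time up to 155 days after the last dose but comparator time for only about 14 days, which understates the OKZ rates

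*Combined protocol and SAP*

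**What the plan says.** Section 9.4.6.1.1 plans subject incidence rates (IR) and event rates (ER) per 100 subject-years (SY) for AESIs, overall and by system organ class and preferred term, under OKZ q4w, OKZ q2w, placebo and adalimumab. Section 7.4.3 lists injection site reactions, and systemic injection and hypersensitivity reactions including anaphylaxis, among the AESIs.

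One denominator rule covers every event type:

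- OKZ time ends at the "date of last dose of OKZ treatment plus 155 days (5 half-lives of study treatment"), capped at last contact when that comes first.
- Comparator time has a different end point: "For placebo and adalimumab treatments, the end of follow-up period will be the day before the start of OKZ treatment".

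For adalimumab, Section 2.3 puts the gap at "the 2 weeks between the last dose of adalimumab in the core study (Week 22) and first dose of OKZ". For placebo in CL04041025, Section 9.4.1 describes subjects who "receive placebo through Week 14 and are re-randomized to OKZ starting at Week 16". For placebo in CL04041022 and CL04041023 the week of the last placebo dose is not given; Section 2.3 says only that "All subjects in this study will receive the first dose of OKZ at Week 24".

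On timing, Section 7.4.3.2 describes acute reactions as arising during the injection or in the 2 hours after it, and adds: "Delayed injection reactions are usually defined as at least 2 of the following 4 signs or symptoms occurring within 1 day to 14 days". Section 7.4.3.5 sets no upper day limit for injection site reactions. No separate at-risk window for injection-linked events appears in the documents.

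**The concern.** Rates per 100 SY are planned so that treatments with very different durations can be put side by side. That works when the person-time counted is time in which the event can plausibly occur. A 155-day tail suits infections or cytopenias, where residual drug matters. Reactions tied to an injection mostly stop arising soon after the last one, and the rest of the tail then enlarges the denominator while adding few events.

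Data capture also thins out in the tail. The Subject Diary is not used in Safety Follow-Up (Section 5.5), and injection site assessment is not listed at the three follow-up visits (Table 1, Section 5.4.3), although adverse events are still recorded there.

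Comparator time has almost no such tail. The distortion therefore falls on one side only and lowers the OKZ figure, for two named AESI categories under the primary safety objective. The exact Poisson limits use the same denominator, so they move down by the same factor.

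**Working it through.** **Inputs.** Last OKZ dose at Week 104 (Section 5.1). First OKZ dose at core Week 0 (OKZ in the core study), Week 16 (CL04041025 placebo) or Week 24 (other placebo, adalimumab). Half-life about 31 days (Section 5.2.2). Risk window after an injection: 14 days (Section 7.4.3.2), with 28 days, the q4w interval, as a sensitivity value.

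**The plan's own figure.** 5 × 31 = 155 days, which reproduces. The last follow-up visit is at 22 × 7 = 154 days.

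**Formula.** Let d be days from first to last OKZ dose and w the risk window. If events occur at a constant rate up to last dose + w and not after, the planned rate is (d + w)/(d + 155) of the at-risk rate. The shortfall is (155 − w)/(d + 155), that is 141/(d + 155) for w = 14 and 127/(d + 155) for w = 28. If the tail rate is a fraction r of the at-risk rate, the shortfall is multiplied by (1 − r). The figures below take r = 0 and full follow-up, so they are ceilings.

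| First OKZ dose | d (days) | d + 155 | d + 14 | Factor | Shortfall, w = 14 | Shortfall, w = 28 |
|---|---|---|---|---|---|---|
| Week 0 | 104 × 7 = 728 | 883 | 742 | 0.840 | 141/883 = 16.0% | 127/883 = 14.4% |
| Week 16 | 88 × 7 = 616 | 771 | 630 | 0.817 | 141/771 = 18.3% | 127/771 = 16.5% |
| Week 24 | 80 × 7 = 560 | 715 | 574 | 0.803 | 141/715 = 19.7% | 127/715 = 17.8% |

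Using 154 days instead of 155 changes the 14-day shortfalls by only about 0.1 percentage point.

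**Comparators.** Adalimumab time is 24 × 7 = 168 days with the last dose at Week 22; CL04041025 placebo time is 16 × 7 = 112 days. Each ends about 14 days after the last dose, so a 14-day cut-off leaves these denominators essentially unchanged. This assumes injections every 2 weeks in these arms.

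**Illustration.** With an assumed at-risk rate of 10 per 100 SY in every arm, the plan would report 8.4, 8.2 or 8.0 for OKZ completers and about 10 for the comparators.

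**IR.** Truncating at first event hardly matters: with 5 to 20% of subjects having an event (assumed), the factor stays at 0.80 to 0.84.

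**Early stoppers, followed in full.**

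- Week-16 or Week-24 starter, last dose 12 weeks after the first: 98/239 = 0.41, a shortfall of 59%.
- OKZ from Week 0: these subjects completed 24 core weeks and took at least one OLE dose, so d is at least about 168 and the factor at least 182/323 = 0.56, a shortfall of at most 141/323 = 44%.
- Last dose 52 weeks after the first: 378/519 = 0.73, a shortfall of 27%.

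**Display threshold.** The most-frequent-TEAE table needs a preferred-term IR of at least 5.0 per 100 SY in some group. An at-risk OKZ rate of 5.9 would appear as 5.9 × 0.840 = 4.96 in Week-0 completers.

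**The case against.** Several points on the other side are sound.

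- **Other displays exist.** Section 9.4.6.1.1 also plans cumulative mean function plots, in which a completer's tail falls only after Week 104, and Section 9.4.6.1 gives incidence and counts with no person-time. But the plots are for AESIs overall and by system organ class, not by reaction category, and early stoppers among later OKZ starters still dilute them. The crude tables cover the OLE groups and do not adjust for duration. Neither corrects the rates.
- **The analysis is descriptive.** Section 9.4 rules out inference. The comparator rows hold only subjects who completed 24 core weeks and entered the OLE; those who left because of reactions are absent. The rows are not like-for-like even without the tail. This limits what the comparison can show, but does not justify adding a one-sided distortion to it.
- **The tail is not shown to be free of risk.** A reader might infer that these reactions cannot occur beyond day 14. The documents do not support that: the delayed window is given as the usual definition, reporting follows the Investigator's judgment, injection site reactions have no upper limit, and hypersensitivity has no stated cut-off for a drug with a half-life of about 31 days. Little risk is the fair description.
- **Last contact caps the tail.** Subjects lost before the final follow-up visit are diluted less.
- **A 14-day cut-off has its own faults.** It could drop a late hypersensitivity event, and it keeps days 15 to 28 of each q4w interval in the denominator. The first is a good reason not to replace the planned rate. The second reflects the regimen while dosing continues, and is why a 28-day sensitivity analysis is useful.

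**Conclusion.** The point stands as a moderate, directional understatement in one set of descriptive tables. For injection site reactions and systemic injection or hypersensitivity reactions, the planned OKZ rates fall short of the at-risk rates by up to about 16.0%, 18.3% and 19.7% for fully followed completers starting OKZ at Week 0, 16 and 24 (14.4% to 17.8% with a 28-day window), and by more for early stoppers.

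This rests on a near-zero event rate beyond the window, follow-up to about 155 days, and a 14-day comparator gap. That gap is documented for adalimumab and CL04041025 placebo and assumed for placebo in CL04041022 and CL04041023. No pooled figure can be given, because subject numbers by treatment sequence and discontinuation rates are not stated.

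Two stronger readings are not supported. One is that the rule will make OKZ appear safer than placebo or adalimumab: the true rates are unknown, nothing is tested, and the comparator rows are a selected group. The other is that a shortfall near 59% is typical: it needs an early stop, full follow-up, and a first OKZ dose at Week 16 or 24. The 155-day tail itself is reasonable for other adverse events.

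**What to change.** Before database lock, add to the SAP for these two AESI categories:

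- an on-treatment IR and ER, with events and person-time both ending at last dose + 14 days (or last contact, if earlier), and comparator time still ending the day before OKZ;
- a sensitivity version at last dose + 28 days, for q4w dosing;
- both shown beside the planned + 155-day rates, so that late hypersensitivity events remain reported;
- a statement that any descriptive comparison with placebo or adalimumab on these events uses the on-treatment rates.

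Keep last dose + 155 days for all other adverse events. The cost is one extra person-time derivation, a footnote explaining the two windows, and slightly less favourable OKZ rates for these events.
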